8.5 Randomisation

At the trial consultation, and once fully consented, participants will be randomised 1:1 to either the control arm (standard information) or to the intervention arm (standard information and SSM App). A block randomisation method, using computer-generated, randomly permuted blocks of size 2, 4, and 6, established by the trial statistician, will be applied. Sets of numbered, sealed envelopes will be prepared, with the order of the sequences verified on completion of the trial.

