2. INTRODUCTION

- 60 This phase II feasibility randomised controlled trial (RCT) tests a novel intervention of the use of a Skin
- 61 Self-Monitoring (SSM) smartphone application ('App'), and self-monitoring monthly reminders, to
- 62 promote timely consulting for skin changes/pigmented skin lesions by people at above-population risk
- 63 of melanoma.

Aims

59

64

65

66 67

68

69

70

71

72

73

74

75

76

77

78

79

- To assess the effect of using a SSM App compared with standard information about detecting skin cancer on the patient interval (time from first noticing skin change to consultation) among patients at above-population risk of melanoma;
- To obtain preliminary estimates of effect across a range of outcome measures to inform selection of the primary outcome for a definitive phase III trial.

Hypotheses

- The MelaTools SSM Trial intervention will increase the number of consultations for pigmented skin lesions in people at above-population risk of melanoma.
- The MelaTools SSM Trial intervention will be acceptable and will reduce the patient interval (including symptom appraisal and help-seeking intervals) in people at above-population risk of melanoma.
- The MelaTools SSM Trial intervention will not cause significant distress or worry in people at above population risk of melanoma.

80 3. METHODS

- 81 Design
- 82 The phase II trial is a multisite individually randomised controlled trial set in 12 general practices across
- 83 Eastern England. Those who meet the eligibility criteria and consent to participate are randomised 1:1
- 84 into either the control or intervention group. Randomisation is being performed using an online system
- provided by the Clinical Trials Unit based at Kings College London.
- 86 Sample size
- 87 The sample size for this Phase II trial is 200. 2000 people will be approached in order to find 400 high risk
- 88 patients, of whom around 200 are expected to consent, as detailed in the trial protocol (Mills et al,
- 89 2017).
- 90 Framework
- 91 This trial is a superiority trial. Comparisons will be presented on this basis. This is a phase II feasibility
- 92 trial and is not powered as a superiority trial for the primary outcome. Estimates will inform the future
- 93 phase III trial.
- 94 Interim analyses and stopping guidance
- 95 No interim analyses are planned.
- 96 Timing of final analysis
- 97 All outcomes will be analysed collectively at the end of the trial.
- 98 Outcomes
- 99 Primary outcomes

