5. TRIAL POPULATION 155 Screening data 156 157 We will report the number of patients assessed for eligibility before recruitment. Eligibility 158 Inclusion criteria 159 160 People aged between 18 and 75 years who own a smartphone (Apple or Android), and, on completion of 161 the Melatools-Q risk assessment tool (Williams et al, 2011), are found to be at increased risk of 162 melanoma. Participants are able to read and write English and to give informed consent. Exclusion criteria 163 Previous diagnosis of melanoma, severe psychiatric or cognitive disorders, or a physical disorder severe 164 165 enough to inhibit the use of a smartphone. Recruitment 166 167 We will report a CONSORT patient flow diagram, including the number of patients 168 assessed for eligibility at screening eligible at screening 169 ineligible at screening * 170 171 eligible and randomised eligible but not randomised * 172 received the randomised allocation 173 174 did not receive the randomised allocation * lost to follow-up * 175 discontinued the intervention * 176 177 randomised and included in the primary analysis randomised and excluded from the primary analysis * 178 179 * reasons will be provided 180 Specifically, for this analysis, we will report in full 181 response rates to each of the PRO surveys (baseline, 6 and 12 months) 182 response rates to the patient interval surveys 183 We will also report 184 item non-response to each survey item among responders 185 Timings for any withdrawals

Baseline characteristics

186

187 We will provide summary statistics on baseline characteristics overall and by arm.

We will describe the median (IQR) consultation rate in the year before randomisation, as well as the median (IQR) age at randomisation and the proportion female. We will further describe the mean (standard deviation) of each of the 9 scale secondary outcome measure, and the baseline distribution of the additional secondary measures which do not form part of a scale.

193 **6. ANALYSIS**

194 Outcome definitions

- 195 Primary outcomes
- 196 Consultation rate
- 197 The number of consultations for skin changes/pigmented skin lesions per person in the 12 months
- 198 following randomisation.
- 199 This will be collected monthly by a search of general practice records. Practices with zero recorded
- 200 consultations at the end of the trial will be higher priority for visits to check for failure to report data.

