 months and 12 months follow-up.

 Those who do not respond to the follow-up questionnaire initially will receive a reminder email, and a phone call reminder.

 Analysis methods

 Analysis of possible consent bias
- 273 Possible consent bias will be assessed by comparing demographics (age, sex) of participants against
- 274 those who declined participation. These comparisons will be performed using a two sample t-test for
- 275 continuous variables and chi-square test for categorical variables.
- 276 Analysis of possible differential attrition
- 277 Possible differential attrition will be assessed by comparing baseline characteristics of those who
- 278 withdraw or die against those who remain in the trial. These comparisons will be performed using a two
- sample t-test for continuous variables and chi-square test for categorical variables.
- 280 Analysis of non-response
- We will compare baseline characteristics of those who do not respond to follow-up questionnaires and
- to patient interval questionnaires with those who do respond. These comparisons will be performed
- using a two sample t-test for continuous variables and chi-square test for categorical variables.
- 284 Analysis of consultation rate
- 285 Data quality checks

287

288

289

290

291292

293

294

- Plot a boxplot of all the consultation rates
- Plot a histogram of all the consultation rates
 - Looking for extreme values, a priori defined as people with 4 or more consultations for suspected skin cancer in a 12 month period. These will be checked for accuracy with the relevant general practice, and either corrected or confirmed accurate and kept in.
- Plot a boxplot of all the consultation rates, by general practice
 - Looking for general practices with oddly high or low consultation rates (although noting that we do expect some general practices to have 0 consultations). The concern will be if there are some practices with high rates across the board, and others with low rates across the board – that may require following up on.
- 296 Analysis planning
- The protocol specifies Poisson regression for this outcome. This is the standard approach for count data.
- 298 It is possible that there is over-dispersion in consultation rates and that other approaches such as
- 299 negative binomial regression would be better. If this is the case, then it will be important to use a more
- appropriate analysis method in the phase III trial. We will report Pearson over-dispersion statistics to

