- inform analysis choice in the phase III trial. For this analysis, we will use Poisson regression.

- 302 Missing data
- There should not be missing data in this outcome as we assume zero consultation rates are true zeros.
- 304 Statistical analysis
- 305 First, we will describe the pre- and post- intervention consultation rates overall and by group,
- 306 summarising using median (IQR) and mean (SD). We will not perform a statistical test, but this will be
- 307 useful information for sample size calculations for the phase III trial.
- The main analysis will be an unadjusted Poisson regression.

Consultation rate, post =
$$\exp(\beta_0 + \beta_1 \times (Intervention))$$

- 309 In Stata code
- 310 glm consult_post i.treat, family(poisson)
- 311 A sensitivity analysis will adjust for demographic information and include a random effect for general
- 312 practice.

Consultation rate, post

=
$$\exp(\beta_0 + \beta_1 \times (Intervention) + \beta_2 \times (Female) + \beta_3 \times (Age in years) + b_1)$$

- Where $b_1 \sim N(0, \sigma_1^2)$ is a random effect to capture GP effects.
- 314 In Stata code
- meglm consult_post i.treat i.female c.age, family(poisson) || practice:
- 316 We will explore the impact of allowing for non-linear associations with age, by introducing a
- 317 changepoint at 65 years.
- 318 Analysis of patient interval among patients who have had a consultation
- 319 Data quality checks

- Plot a boxplot of all the patient intervals
- 321 Plot a histogram of all the patient intervals
- We know from Lyratzopoulos et al (2015) that the quartiles of the patient interval for a different sample of patients with melanoma were Min: 0, Q1: 0, Q2: 21, Q3: 69, pct90:
- 324 234 days. We will have concerns about either data quality or generalisability if more
- 325 than 25% of patients have a patient interval of 80+ days.
- 326 Analysis planning
- 327 The protocol specifies standard linear regression, and includes flexibility on the particular analysis in
- 328 case data are highly skewed.
- 329 We will use linear regression to analyse these data. We will also tabulate consultations by trial arm and
- whether the patient interval was more (or less) than 21 days.

- 331 Missing data
- We expect missing data in this outcome, because it is based on a survey of patients and not all patients
- will respond.
- In the first instance, we will compare rates of missing data between the intervention and control groups.

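### The main consultation-rate model leaves out practice: if allocation is unstratified and practices differ, the rate ratio is noisier than it need be and its Poisson interval too narrow

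*Protocol*

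**What the plan says.** On allocation, protocol section 8.5 states: "A block randomisation method, using computer-generated, randomly permuted blocks of size 2, 4, and 6, established by the trial statistician, will be applied". It continues: "Sets of numbered, sealed envelopes will be prepared, with the order of the sequences verified on completion of the trial". It does not say whether there is one set per practice. SAP section 3 (Design) says: "The phase II trial is a multisite individually randomised controlled trial set in 12 general practices across" Eastern England, and that an online system is used. It names no strata.

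On recording, protocol section 8.7.2 has each practice search its own records monthly, with a final audit after the trial. SAP section 6 says that practices with zero recorded "consultations at the end of the trial will be higher priority for visits to check for failure to report data", and that visiting all 12 may not be possible. Its data quality checks note that "we do expect some general practices to have 0 consultations", but treat rates that are uniformly high or low in a practice as something to follow up. Under missing data, a zero is taken as a true zero.

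On analysis, SAP section 6 states: "The main analysis will be an unadjusted Poisson regression". The code has the arm term only. Then: "A sensitivity analysis will adjust for demographic information and include a random effect for general" practice. That model also contains sex and age. Poisson is kept whatever over-dispersion is found. Table 3 shows the unadjusted model. The practice model appears only in Appendix 2 Table 2.

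**The concern.** The count for each participant depends on how often that person consults and on how well that person's practice finds and reports consultations. The SAP takes the second seriously enough to plan visits and plots by practice. Neither the described allocation nor the main model deals with it.

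Under a single unstratified list, the arms can differ by chance in how many participants come from high-recording and low-recording practices. That difference goes straight into the rate ratio. The Poisson standard error assumes that a count varies only as a Poisson variable with the arm's mean, so it does not allow for this extra spread. The estimate, its interval and its p-value are what Table 3 reports and what is carried into phase III planning.

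**Working it through.** **The plan's own figure.** Protocol section 9.4: 1,600 × 0.25 × 0.50 = 200, which reproduces. With the SAP's 12 practices, 200/12 = 16.7 participants each. The documents give no consultation rate, no between-practice spread and no number of zero practices, so all three are assumed below.

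**Step 1: imbalance within practices.** Under one list, the arm difference in a practice of 16.7 has SD of about √16.7 = 4.1. In simulation the worst practice has a median difference of 7 participants, against 2 with per-practice lists.

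**Step 2: effect on the rate ratio.** Assume a quarter of practices at zero and a coefficient of variation of 0.5 among the rest. Imbalance alone gives the log rate ratio an SD of 0.113, so a 95% range of exp(±1.96 × 0.113) = 0.80 to 1.25. With per-practice lists the SD is 0.027, so 0.95 to 1.05.

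**Step 3: set against Poisson noise.** The model SE is √(1/a + 1/b), where a and b are the event totals in the two arms. At 0.3 per person-year its simulated mean is 0.266. Adding the imbalance gives √(0.266² + 0.113²) = √(0.0708 + 0.0128) = 0.289, close to the simulated 0.294. The imbalance share of variance is 0.0128/0.0835 = 15%. At 0.1 per year (SE 0.480) it is 0.0128/0.2432 = 5%. At 0.5 per year (SE 0.204) it is 0.0128/0.0544 = 24%.

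**Step 4: simulation under no effect** (3,000 runs per row, 12 equal practices, unstratified list, practice fixed effects standing in for the random intercept):

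| Rate | Practices at zero | SD, arm only | Mean SE | Type I | SD, with practice | Type I | Variance change |
|---|---|---|---|---|---|---|---|
| 0.1 | 25% | 0.528 | 0.480 | 4.9% | 0.523 | 4.0% | −2% |
| 0.3 | none, no differences | 0.267 | 0.262 | 4.9% | 0.276 | 5.0% | +7% |
| 0.3 | 25% | 0.294 | 0.266 | 6.8% | 0.274 | 4.6% | −13% |
| 0.5 | 25% | 0.232 | 0.204 | 7.7% | 0.211 | 4.8% | −17% |
| 0.3 | 50% (extreme) | 0.326 | 0.268 | 10.4% | 0.279 | 4.5% | −27% |

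Variance change is (SD with practice / SD arm only)² − 1. The mean log rate ratio lies within 0.015 of zero in every scenario run, so there is no bias.

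**Step 5: unequal practices at 0.4 per year.** With a practice log-rate SD of 0.5 and 3 of 12 practices at zero, the SD of the log rate ratio falls from 0.254 to 0.234, and 1 − (0.234/0.254)² = 15% less variance. Type I error goes from 7.2% to 4.7%. With SD 0.8 and no zero practice, type I error goes from 7.9% to 4.3%. Two further sets of runs with 3 zero practices, differing in detail, give:
- SD 0.5: 0.294 to 0.280 (9% less variance) and 0.258 to 0.240 (13%).
- SD 0.8: 0.322 to 0.289 (19%) and 0.282 to 0.249 (22%). In the second of these, type I error as written is 9.7%.

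At 0.2 per year, SD 0.5 and no zero practice, there is essentially no gain.

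**Step 6: cost when practices do not differ.** Fixed effects cost about 7% in variance (second table row). A practice-frailty model, closer to the SAP's random intercept, costs nothing: SD 0.220 with and without it.

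**Step 7: if lists are in fact per practice.** In the scenarios with practice differences, the arm-only model then has type I error of 3.9 to 5.6%. At 0.3 per year with 25% zeros its SD is 0.268, against 0.267 adjusted. The problem largely disappears.

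**The case against.** **Stratification is not ruled out.** The absence of strata is read from silence. Sets of envelopes may mean one set per practice, and Step 7 shows that this would remove most of the problem. This stands, so the point is conditional.

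**Expected zeros do not show that practices differ.** At a common rate of 0.1, an average practice records none with probability exp(−0.1 × 16.7) = 0.19, or about 12 × 0.19 = 2.3 practices by chance. This stands, and at that rate adjusting gains almost nothing. At 0.4 per year the same probability is exp(−6.67) = 0.001, so zero practices would then point to real differences or under-recording.

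**Under-recording is already tackled.** The final audit (protocol sections 8.7.2 and 8.8.2), the priority visits and corrections before unblinding all reduce it. They may not reach every practice by visit, and they leave true differences between practices untouched.

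**The practice model is already prespecified,** with its random-effect SD reported, in a trial not powered for superiority. True, but Table 3 still gives the arm-only ratio with an interval and p-value, and a reader will take that as the result.

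**Stronger readings to avoid.** A reader might infer that the rate ratio is biased towards or against the App. The simulations show no bias; a misleading ratio would be chance error in one trial. A reader might also infer that allocation should have been stratified by practice. The documents do not establish that it was not. Per-practice lists with blocks as small as 2, in a trial where the nurse delivers the arm openly, would also make the next allocation easier to guess.

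**Conclusion.** The point holds in conditional form. The main model omits practice, and the documents name no stratification. If allocation is unstratified and practices differ, the rate ratio carries avoidable variance and its plain Poisson interval is too narrow.

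Under assumed inputs the effect is negligible at about 0.1 to 0.2 consultations per person-year. At 0.4 per year with moderate to large practice differences, adjusting removes roughly 10 to 20% of the variance and returns type I error from about 7 to 8% to about 5%. Harsher assumptions give more. The simulations in Steps 4 and 6 used close stand-ins for the SAP's normal random intercept, so the direction is firmer than the exact figures. For an unpowered phase II trial this is a moderate point, worth making because the remedy is already written.

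**What to change.** In SAP section 6, make the main consultation-rate model a Poisson regression with arm and the practice random intercept. This is the existing sensitivity code without sex and age: `meglm consult_post i.treat, family(poisson) || practice:`. Show it in Table 3 and report the arm-only model as the sensitivity analysis. With a log link and a random intercept, the rate ratio keeps its meaning. A robust or scaled variance on the arm-only model would repair the interval but not recover the precision.

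The cost is one line of code and one table, with no new data and essentially no loss of precision if practices do not differ. The change belongs before unblinding. If results are already known, give both models equal prominence and say when the choice was made.

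Separately, reconcile the sealed envelopes in protocol section 8.5 with the online system in SAP section 3, and state whether lists are per practice. The allocation itself need not change.

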8.6 Trial Consultation

8.6.1 Control and Intervention groups

The research nurse will start all the trial consultations by taking written informed consent. Participants will then complete the baseline questionnaire on an iPad. Next, the research nurse will deliver the standardised advice on skin cancer prevention, and provide written or emailed supporting information sheets. The follow-up procedure will be explained (when they will receive questionnaires, how long they have to complete them, how they can receive help answering questions etc.). Participants who fail to attend the consultation will be contacted for another appointment.

8.6.2 Intervention group only

The research nurse will help intervention group participants to download the SSM App onto their smartphone; they will go on to give instructions on its use, again supported by written or emailed information sheets. Finally, each intervention participant will be given an Apple Apps store/Google Play voucher to pay for the App. A monthly SMS will be sent to these participants to prompt them to think about symptoms and to use the SSM App.

8.7 Follow-up

8.7.1 Participants

Six months post-study consultation, all participants will be sent an email reminding them of the study, and a link to an online questionnaire. The questionnaire will be identical to the baseline questionnaire (omitting the demographic data), and will take up to 15 minutes to complete. The same will happen 6 months later, at 12 months post consultation. If either the 6 and/or 12-month follow-up questionnaire have not been returned after 2 weeks, a further reminder will be sent; this will be repeated after a further 2 weeks. On return of the questionnaire the HADS will be scored; if the participant scores \geq 10 on the anxiety scale or \geq 8 on the depression scale, a letter will be sent to notify their GP.

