8.8 Measures

8.8.1 Patient Reported Outcome Measures (PROMs)

For all participants, these data will be collected at baseline, 6 months and 12 months post-trial consultation:

- a. Demographics and clinical variables: age, gender, marital status, postcode, highest education level, occupation, past history of skin cancer (melanoma, SCC, BCC), skin and hair type (density of freckles on arms before age 20, natural hair colour at age 15, number of severe sunburns aged 2-18), number of raised moles on both arms, measured at baseline only.
- b. Sun protection habits scale: developed by Glanz et al in the US for a multicomponent skin cancer prevention programme, this comprises 5 items measured using a 4 point Likert scale, and relating to use of sun protection, sun and sunbed habits, and episodes of sunburn in the previous year (27).
- c. Skin Self-Examination benefits and barriers scale: validated by Manne and Lessin in the US among melanoma survivors, and developed from previous work on mammography and family members of patients with colorectal cancer (28). The benefits scale has seven items (α =.71) and the barriers scale has ten items (α =.74).

411 d. Melanoma Worry Scale (MWS): validated by Moye et al in the US (29), an adapted from 412 the Breast Cancer Worry Scale (30), this measure comprises four items, scored 1 to 4, with 413 possible scores ranging from 4 to 17, and higher scores indicating higher levels of worry.

e. Perceived Melanoma Risk: drawn from Manne and Lessin's measures (28), these two items have been widely used for melanoma and other cancer risk assessments to assess estimated percent risk of developing melanoma, and perceived risk compared with a person of the same age (relative risk).

f. Self-Efficacy for consulting without delay: A 10-item self-completed scale summed to score 10-100, was used in a primary care trial for lung symptoms, and showed good internal reliability (Cronbach α =0.85) (21, 31, 32). It has been adapted for this study, and reduced to 8 items.

g. Hospital anxiety and depression scale (HADS): This 14-item self-completed scale has been widely used to measure distress and has been extensively validated and shown to perform well in a wide range of populations (mean Cronbach α = 0.82; sensitivity and specificity 0.80) (33).

h. SF-12 Quality of life scale: a 12-item version of the SF-36 that is widely used and validated to measure functional health and well-being.

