          4. Melanoma Worry Scale (Moye et al, 2015)
231
                   - Higher score = more worry, range 4-17 (sum of Qs)
232
          5. Self-efficacy for consulting without delay (Smith et al, 2012; Smith et al, 2013)
                   - Higher score = more confident about consulting quickly, range 8-80 (sum of Qs)
233
234
          6. HADS-D (Depression) (Zigmond and Snaith, 1983)
235
                   - Higher score = more depressed, range 0-21 (sum of Qs)
236
          7. HADS-A (Anxiety)
237
                   - Higher score = more anxious, range 0-21 (sum of Qs)
238
          8. Skin Self-Examination Benefits (Manne and Lessin, 2006)
                   - Higher score = more benefits, range 7-35 (sum of Qs)
239
240
          9.
             Skin Self-Examination Barriers
                   - Higher score = more barriers, range 10-50 (sum of Qs)
241
242
243
       There are several additional secondary outcomes which will be analysed on their own, rather than as
244
       scales.
245
               Did you practice sun protection last year?
                  o "Rarely or never", ..., "Always"
246
              How likely are you to practice sun protection in the coming year?
247
                   "Not at all likely", ..., "Extremely likely"
248
249
               Have you ever used sunbeds?
250
                   o "Yes" / "No"
                   o EDIT – 1 February 2019 – this outcome was excluded from analysis.
251
252
              How many times have you been sunburnt in the last year?
                   o 0, 1-2, "3-5", "More than 5"
253
254
              Compared with other people, do you think your chances of getting melanoma are lower or
255
               higher?
                   o "Much lower", ..., "Much higher"
256
              What do you think your lifetime risk of melanoma is?
257
258
                   o 0% to 100%
259
               Have you downloaded any apps [for detecting melanoma]?
                   "No" / "Yes"
260
261
              If yes, name?
262
                   o [freetext]
263
              How often have you used this app?
                   o "Never", "Once", "Once every 6 months", "Once every 3 months", "Every month"
264
```

We will describe the distribution of responses to these questions overall and by arm, at baseline, 6

265

266

months follow-up and 12 months follow-up.

- These will be collected from patients using questionnaires sent out at baseline (pre-randomisation), 6

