- 390 There are several other secondary outcomes which do not form part of scales.

391 392 393 394	Statistical analysis and missing data Analysis for these items will be entirely descriptive. We will quantify the amount of missing data, and then describe the distribution of these responses at 0,6,12 months follow-up by trial arm (without any statistical testing).
395 396	If we do see apparent differences then this may suggest that one of these is a good outcome variable for use in the Phase III.
397	We will not present p-values for differences on these outcomes.
398 399	Analysis of melanoma incidence This is just for context, and of course is a useful data quality check.
400 401 402	We will request from PHE ODR the full count of incident cases across these practices in 2013 to 2015 and nationally, without any demographic information. We will then calculate the rate as the total number of cases divided by the total practice list size / population of England.
403 404	This avoids any identifiability concerns around patients registered at these practices who have not consented to take part in the trial.

405	Harms
406	No specific adverse event information has been collected for this trial, beyond outcome measures
407	already described.
408	Statistical software
409	All analysis will be carried out in Stata v15.
410	Additional analyses
411	We have described several exploratory analyses looking for evidence of differential impact to help in
412	design of the analysis for the phase III trial.
413	

REFERENCES

414

423

424

425

426

427

428

429

430

431

432

433

434

435

[figure not shown]
436

437

445

- 420 Manne S and Lessin S (2006) Prevalence and correlates of sun protection and skin self-examination 421 practices among cutaneous malignant melanoma survivors. *J Behav Med* **29**: 419-34, 422 doi:10.1007/s10865-006-9064-5

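### At 6 months the two sun items with one-year recall look back about equally before and after randomisation, so their between-arm contrast is attenuated; the 12-month reading is not affected

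*Protocol*

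**What the plan says.** **Timing.** Protocol section 8.5 places allocation at the trial consultation: "At the trial consultation, and once fully consented, participants will be randomised 1:1". Section 8.7.1 starts the follow-up clock at the same visit: "Six months post-study consultation, all participants will be sent an email", and then "The same will happen 6 months later, at 12 months post consultation". Of the form itself it says: "The questionnaire will be identical to the baseline questionnaire (omitting the demographic data").

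**Recall period.** The statistical analysis plan text that follows the protocol (section 6, Secondary outcomes) lists, among the items analysed on their own, "How many times have you been sunburnt in the last year" and "Did you practice sun protection last year". Its scoring appendix labels both with a one-year period (items 1.5 and 1.2) and keeps them apart from the five scored items of the Sun Protection Habits scale. Protocol section 8.8.1(b) also describes "episodes of sunburn in the previous year".

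**Use.** Planned Table 5 shows both items by arm at 6 and at 12 months. Section 6 of the analysis plan treats this group of items descriptively, with no p-values, but says that apparent differences "may suggest that one of these is a good outcome variable for use in the Phase III". Nothing in the text shortens the recall period at 6 months or limits these two items to 12 months.

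**The concern.** An outcome should describe the time after allocation. A question covering a full year, asked six months after allocation, also takes in six months that the intervention could not have changed. A participant sunburnt in that earlier half cannot truthfully answer zero at 6 months, whatever happened later.

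Protocol section 6.2 (Aim 2) wants preliminary effect estimates to guide the choice of the phase III primary outcome, and these items are named as possible candidates. A 6-month column that is attenuated by construction could understate an early difference. A larger difference at 12 months than at 6 could also be read as an effect building up when part of it comes from the changing make-up of the recall window. Sun exposure is seasonal, so the attenuation also varies with the date of entry, and a reader of Table 5 has no means of correcting for it.

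**Working it through.** The documents give no figure for this point, so there is none to reproduce. The check is date arithmetic.

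**Inputs from the documents**
- Randomisation at month 0, at the trial consultation (protocol 8.5).
- Questionnaires at months 6 and 12 (protocol 8.7.1).
- Recall of one year (analysis plan section 6 and scoring appendix), taken as the 12 months before completion.
- Reminders at 2 weeks and again 2 weeks later (protocol 8.7.1), so a return 28 days late is plausible.

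**Assumptions**
- Participants answer for the stated window.
- Month of entry is not documented, so all months were tried.
- The length of the sun season is not documented, so three definitions were tried.

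**Step 1: share of the recall window before randomisation**

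Share = (12 − months since randomisation) / 12.
- At 6 months: (12 − 6)/12 = 50% (49.7% to 50.4% by calendar days). With a return 28 days late, 42% to 43%.
- At 12 months: (12 − 12)/12 = 0%, on time or late.

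**Step 2: share of the sun season before randomisation, 6-month form returned on time**

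Share = season days between the start of the window and the entry date, divided by all season days in the window. For example, entry on 1 July puts the form at 1 January. The earlier half of the window is January to June, which holds May and June: (31 + 30)/153 = 40% of a May to September season.

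| Entry | June–Aug | May–Sept | April–Sept |
|---|---|---|---|
| 1 January | 67% | 60% | 50% |
| 1 April | 0% | 0% | 0% |
| 1 July | 33% | 40% | 50% |
| 1 September | 100% | 80% | 84% |
| 1 October | 100% | 100% | 100% |
| 1 November | 100% | 100% | 84% |

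With a return 28 days late, entry on the first of September, October or November gives 68% to 100%.

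**Step 3: what this does to a contrast**

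Let p be the share of control-arm events in the window that fall before randomisation, and r the true relative reduction afterwards. Setting the control total to 1, the intervention total is p + (1 − p)(1 − r), so the reduction seen is 1 − [p + (1 − p)(1 − r)] = (1 − p)r. At p = 0 all of r is seen, at p = 0.5 half of it, and at p = 1 none.

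This is exact only for a mean count. Sunburn is recorded in four bands and sun protection as a frequency rating, so the formula gives the direction and a rough size for sunburn, and only the direction for the rating.

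**The case against.** **Stakes are low.** Both items are secondary, described without testing, and feed no model, sample size or primary outcome. That stands, and it means that loss of power is not a relevant measure here.

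**A clean reading sits in the same table.** The 12-month column is free of the problem, so a candidate that shows a difference there is not lost. That also stands. What remains is that nothing tells the reader to prefer that column.

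**The error is conservative.** Randomisation balances the period before allocation, so the overlap adds no systematic difference between arms. Agreed.

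**Little difference may be expected anyway.** Both arms receive the same prevention advice (protocol 8.3.2 and 8.6.1), and none of the hypotheses in section 6.3 concerns sun behaviour. This rules out attaching an assumed effect size to the loss. It does not remove the attenuation of whatever difference exists.

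**Identical wording at every visit is a defensible choice.** It keeps readings comparable in form, but the content of the window still changes between 6 and 12 months.

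Four stronger readings are tempting and not supported:
- *That an early effect would disappear.* Under an even spread of events over the year it would appear at about half size. Near-complete loss applies only to autumn entry, and the documents do not say how many entered then.
- *That growth from 6 to 12 months would be an artefact.* It could be partly so. The plan specifies a time-by-arm interaction only for the nine scales, not for these items.
- *That the modelled Sun Protection Habits score is diluted.* No recall stem is shown for its five items. The sentence in section 8.8.1(b) attaches the previous year to sunburn and does not settle the point for the scale.
- *That trial conclusions are biased.* No primary result or p-value depends on these items.

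**Conclusion.** The point holds for two items: sunburn in the last year and the single question on practising sun protection. At 6 months about half of their recall window (42% to 50%, depending on return date) precedes randomisation, so the 6-month contrast between arms is attenuated towards no difference. Under an assumed May to September season the share of the season affected runs from none for entry on 1 April to all of it for entry on 1 October. The recruitment months are not given, so the average for this trial cannot be stated.

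The conclusion rests on reading the stems as the 12 months before completion, which the scoring labels support, and on participants answering accordingly. The 12-month reading is sound. The consequence is modest: a misleading 6-month column for two descriptive items which the plan nevertheless allows to influence the choice of phase III outcome.

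**What to change.** - Name the 12-month reading as the outcome time point for these two items. Its window lies wholly after randomisation and spans a full year, as the baseline window does.
- Remove their 6-month columns from Table 5, or footnote them as overlapping the period before randomisation and not to be used for judging early effect or change over time. This also works if the data are already collected.
- If a 6-month value is wanted, ask about the time *since your trial consultation*, compare arms only, and label it as not comparable with baseline or 12 months. For an October entrant this window would contain no summer.
- Check the stem of the five-item Sun Protection Habits scale. Apply the same change only if it carries a one-year recall.

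The cost is two table rows or two question stems, and the loss of a like-for-like 6-month value on two items. Sample size, visits and the primary analyses are unchanged.
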